5.2. Subject identification and randomisation

5.2.1. Subject identification

Subject identification numbers will be assigned sequentially to the subjects who have consented to participate in the study, according to the range of subject identification numbers allocated to each study centre.

In order to allow for proper control of recruitment as per the Step 1 and Step 2 recruitment targets, consented subjects will be registered in the SBIR application.

5.2.2. Randomisation of treatment

5.2.2.1. Randomisation of supplies

The randomisation of supplies within blocks will be performed at GSK, using MATerial EXcellence (MATEX), a program developed for use in Statistical Analysis System (SAS[®]) (Cary, NC, USA) by GSK. Entire blocks will be shipped to the study centres/warehouse(s).

To allow GSK to take advantage of greater rates of recruitment than anticipated at individual centres in this multi-centre study and to thus reduce the overall study recruitment period, an over-randomisation of supplies will be prepared.

5.2.2.2. Treatment allocation to the subject

The treatment numbers will be allocated by dose.

5.2.2.2.1. Study group and treatment number allocation

The target will be to enrol approximately 500 eligible subjects who will be randomly assigned to four study groups in a (1: 1: 1: 1) ratio (~125 subjects in each group).

Allocation of each subject to a study group at the investigator site will be performed using SBIR. The randomisation algorithm will use a minimisation procedure accounting for age (18 - 32 years or 33 - 45 years) and centre. Minimisation factors will have equal weight in the minimisation algorithm.

At Visit 1, after having fully checked the eligibility of the subject, the site staff in charge of the vaccine administration will access SBIR. Upon selecting the subject identification number previously entered in the application, the randomisation system will determine the study group and will provide the treatment number to be used for vaccination.

The number of the administered treatment must be recorded in the eCRF on the Vaccine Administration screen.

When SBIR is not available, please refer to the SBIR user guide or the Study Procedures Manual (SPM) for specific instructions.

5.3. Method of blinding

Given the different presentation of the placebo and the investigational RSV vaccines, a double-blinded study design is not possible. Refer to Section [1.5.6](#) for more information on study blinding.

Data will be collected in an observer-blinded manner up to Day 91 (Visit 5). During this time, vaccine recipients and those responsible for the evaluation of any study endpoints will be unaware of which vaccine was administered. To achieve this, vaccine preparation and administration will be done by authorised medical personnel who will not participate in any of the study clinical evaluations. Additionally, vaccine recipients will receive the same volume (0.5 mL) of the study product on Day 1.

Analyses for the iSRC review will be performed by an independent statistician to ensure that the study team remains blinded to individual subject listings. Refer to Section [10.11](#) for more information on analyses.

The laboratory in charge of the laboratory testing will be blinded to the treatment, and codes will be used to link the subject and study (without any link to the treatment attributed to the subject) to each sample.

5.4. General study aspects

Supplementary study conduct information not mandated to be present in this protocol is provided in the accompanying SPM. The SPM provides the investigator and the site personnel with administrative and detailed technical information that does not impact the safety of the subjects.

5.5. Outline of study procedures

Table 4 List of study procedures

Epoch	001		002			003			Unsch Visit
	Type of contact	Screening Visit	Visit 1	Visit 2	Visit 3	Visit 4	Visit 5	Contact 1	
Time point(s)	Day -7 to Day 1	Day 1	Day 8	Day 31	Day 61	Day 91	Day 181		
Sampling time point(s)	Pre-Vacc	Vacc	Post-Vacc	Post-Vacc	Post-Vacc	Post-Vacc	Post-Vacc		
Informed consent	●								
Assign subject number	●								
Register subject in SBIR	0								
Check inclusion/exclusion criteria	●	0 ¹							
Collect demographic data	● ²								
Medical history	0	●							
Physical examination ³	●	● ¹	●	0 *	0 *	0 *		0 *	
Urine pregnancy test ⁴	●	● ¹							
Pre-vaccination body temperature		●							
Distribution of subject card	0								
Blood sampling for humoral immune response (~30 mL) ⁵	●		●	●	●	●			
Blood sampling for haematology/ biochemical analysis (~5.5 ml) ⁵	●		●	●				●	
Study group and treatment number allocation (SBIR)		0							
Vaccine administration		●							
Recording of administered treatment number		●							
60 minutes post vaccination observation period		0							
Training on use of diary cards		0	0						
Distribution of diary cards ⁶		0	0						
Collection of diary cards			0	0					
Diary card transcription by investigator			●	●					
Recording of solicited adverse events		●	●						
Recording of unsolicited adverse events		●	●	●				●	
Recording of AE leading to withdrawal		●	●	●	●	●	●	●	●
Recording of serious AE ⁷	●	●	●	●	●	●	●	●	●
Recording of pregnancies		●	●	●	●	●	●	●	●
Recording of concomitant medications/vaccinations		●	●	●	● ⁸				

CONFIDENTIAL

208068 (RSV MAT-001)
Protocol Final Version 2

Epoch	001	002			003			Unsch Visit
Type of contact	Screening Visit	Visit 1	Visit 2	Visit 3	Visit 4	Visit 5	Contact 1	Unsch Visit
Time point (s)	Day -7 to Day 1	Day 1	Day 8	Day 31	Day 61	Day 91	Day 181	Unsch Visit
Sampling time point(s)	Pre-Vacc	Vacc	Post-Vacc	Post-Vacc	Post-Vacc	Post-Vacc	Post-Vacc	
Record any intercurrent medical conditions			●	●	●	●	●	●
Check for interest in participating in future booster study	O						●	
Screening conclusion	●							
Investigator sign-off on eCRF before analysis						●	●	
Study Conclusion							●	

Vacc: vaccination.

- is used to indicate a study procedure that requires documentation in the individual eCRF.
- is used to indicate a study procedure that does not require documentation in the individual eCRF

¹ When Screening Visit and Visit 1 are performed on the same day, Inclusion and Exclusion Criteria check, Physical examination and Urine pregnancy test will not be repeated.

² Date of birth (month and year or year only, as per local regulations), race, ethnicity and childbearing potential (if subject not of childbearing, the specific reason should be documented in the eCRF: hysterectomy, ovariectomy, post-menopause, pre-menarche or other)

³ Physical examination including resting vital signs (blood pressure, heart rate and respiratory rate, temperature) after at least 10 minutes of rest. Weight, height and BMI will only be collected at Screening. * Physical examination at Visits 3, 4 and 5, as well as any unscheduled visit, will be performed only if deemed necessary by the investigator

⁴ Only for women of childbearing potential. Urine pregnancy test is sufficient to determine the eligibility to enter the study. Serum pregnancy test (instead of urine test) may be performed if required by country, local or ethics committee regulations.

⁵ Method, cut-off, and laboratory locations are defined in Section 5.7.

⁶ Two diary cards will be distributed. The first one will be distributed at the day of vaccination and will be used for recording solicited and unsolicited AEs, and concomitant medications/products on the day of vaccination and for 6 subsequent days. The second one will be distributed at Visit 2 (Day 8) and will be used for recording unsolicited AEs and concomitant medications/products and vaccinations from Day 8 to Day 30.

⁷ For Screening and Visit 1 (prior to study vaccine administration), only those SAEs that are considered related to study participation need to be recorded.

⁸ Recording of Concomitant medications/vaccinations/products as described in Section 6.6.

Note:

The dashed line border between Screening and Visit 1 indicates the ability for investigator/subject to be screened and vaccinated on the same day, when possible. Prior to vaccination all study procedures in the screening visit must be recorded in eCRF and signed by investigator.

Table 5 Intervals between study visits

Interval	Optimal length of interval ¹	Allowed interval ²
Screening Visit → Visit 1 (Day 1)	≤7 days	0 – 7 days
Visit 1 (Day 1) → Visit 2 (Day 8)	7 days	7 - 10 days
Visit 1 (Day 1) → Visit 3 (Day 31)	30 days	30 - 45 days
Visit 1 (Day 1) → Visit 4 (Day 61)	60 days	56 – 70 days
Visit 1 (Day 1) → Visit 5 (Day 91)	90 days	86 - 100 days
Visit 1 (Day 1) → Contact 1 (Day 181)	180 days	165 - 195 days

¹ Whenever possible the investigator should arrange study visits within this interval.

² For a study visit where a sample is collected, subjects will not be eligible for inclusion in the Per Protocol (PP) cohort for analysis of immunogenicity if the visit takes place outside this interval.

5.6. Detailed description of study procedures

5.6.1. Study procedure timings

When the Screening Visit and Visit 1 are performed on the same day, the following study procedures will not be repeated:

- Physical Examination (note: temperature [including pre-vaccination temperature] will only be measured once but recorded twice).
- Urine (or serum, if required) Pregnancy test.

5.6.2. Informed consent

During the Screening Visit the signed/witnessed/ thumb printed informed consent of the subject must be obtained before study participation.

Refer to Section 5.1 for the requirements for informed consent, as appropriate.

5.6.3. Subject number allocation and Registration in SBIR- “subject planning” module

Upon signature of the ICF and a first check on eligibility, the subject will be assigned a subject number (refer to section 5.2.1).

The assigned subject number must be recorded in the eCRF.

In addition, the site staff will register the subject into the SBIR application. This will allow to properly control recruitment per the established Step 1 and Step 2 recruitment targets.

5.6.4. Check inclusion and exclusion criteria

Check all inclusion and exclusion criteria as described in Sections 4.2 and 4.3 during the Screening Visit and verify prior to randomisation.

5.6.5. Collect demographic data

During the Screening Visit, record demographic data such as date of birth (month and year or year only, as per local regulations), race and ethnicity as well as information on subject's childbearing potential (if subject is not of childbearing potential, the specific reason should be documented: hysterectomy, ovariectomy, post-menopause, pre-menarche or other) in the subject's eCRF.

5.6.6. Medical history

Obtain the subject's medical history by interview and/or review of the subject's medical records and record any pre-existing conditions or signs and/or symptoms present in the subject prior to the study vaccination (Visit 1) in the eCRF.

5.6.7. Physical examination

During the Screening Visit, Visit 1 and Visit 2, perform a physical examination of the subject, including assessment of resting vital signs: systolic and diastolic blood pressure, heart rate, respiratory rate and temperature, after at least 10 minutes of rest. In addition, at Screening only, collect height, weight and BMI. Collected information needs to be recorded in the eCRF.

At subsequent study visits, perform a physical examination only if the subject indicates during questioning that there might be some underlying pathology(ies) or if deemed necessary.

Treatment of any abnormality observed during physical examination has to be performed according to local medical practice outside this study or by referral to an appropriate health care provider.

5.6.8. Pregnancy test

Female subjects of childbearing potential are to have a pregnancy test during the Screening Visit and Visit 1 (prior to study vaccine administration). The study vaccines may only be administered if the pregnancy test is negative.

Urine pregnancy test is sufficient to determine the eligibility to enter the study, however, serum pregnancy test (instead of urine test) may be performed if required by country, local or ethics committee regulations.

Note: The pregnancy test must be performed even if the subject is menstruating at the time of the study visit.

5.6.9. Check contraindications, warnings and precautions to vaccination

Contraindications, warnings and precautions to vaccination must be checked at the beginning of the vaccination visit. Refer to Sections 6.5 and 6.6 for more details.

5.6.10. Assess pre-vaccination body temperature

Record the body temperature of the subject prior to study vaccination. The preferred route for recording temperature in this study will be oral using the provided GSK thermometers.

If the subject has fever (defined as temperature $\geq 38.0^{\circ}\text{C}/100.4^{\circ}\text{F}$ regardless of the location of measurement) on the day of vaccination, Visit 1 can be rescheduled within the allowed interval for this visit (see [Table 5](#)).

If meeting the allowed interval between Screening and Visit 1 in such cases is not possible, subject may be re-screened at a later date (per investigator's discretion).

5.6.11. Study group and treatment number allocation

Study group and treatment number allocation will be performed as described in Section [5.2.2](#). The number of the administered treatment must be recorded in the eCRF.

5.6.12. Blood sampling for safety or immune response assessments

A volume of ~ 5.5 mL of whole blood should be drawn from all subjects for analysis of the haematology/biochemistry parameters at Screening, Visit 2, Visit 3 and Unscheduled Visits (if any). In the event any re-test is needed; as per investigator discretion, (e.g. laboratory abnormalities) the volume required will also be ~ 5.5 mL. Haematology and biochemistry assessments will be performed in the investigator's laboratory as per local practice (see [Table 8](#) and [Table 9](#)).

A volume of ~ 30 mL of whole blood should be drawn from all subjects at Screening, Visit 2, Visit 3, Visit 4 and Visit 5 for analysis of humoral immune responses (see [Table 7](#) and [Table 10](#)).

Refer to the SPM for details on blood sample handling.

5.6.13. Study Vaccine administration

After completing all prerequisite procedures prior to vaccination, administer one dose of study vaccine intramuscularly in the deltoid of the non-dominant arm. In case of anatomical features, medical indication or skin colouration (e.g. tattoos) preventing vaccination in the non-dominant arm, the vaccine may be administered in the dominant arm. Refer to Section [6.3](#) for information on the dosage and administration of the vaccine.

If the investigator or delegate determines that the subject's health on the day of administration temporarily precludes vaccines administration, the vaccination visit will be rescheduled within the allowed interval (refer to [Table 5](#)).

Vaccination in Step 1 will be limited to 10 subjects a day for the first 30 subjects. These subjects should be vaccinated sequentially and at least 60 minutes apart.

5.6.14. 60 minutes post-vaccination observation

All subjects across all steps will be observed closely at least 60 minutes following study vaccination, with appropriate medical treatment readily available in case of anaphylaxis and syncope related issues/injuries.

5.6.15. Distribution of Subject Card

For information regarding the Subject Card, please refer to Section [8.9](#).

5.6.16. Check and record concomitant medication/vaccination and intercurrent medical conditions

Concomitant medication/vaccination must be checked and recorded in the eCRF as described in Section [6.6](#).

Intercurrent medical conditions must be checked and recorded in the eCRF as described in Section [6.7](#).

5.6.17. Recording of AEs, SAEs and pregnancies

- Refer to Section [8.3](#) for procedures for the investigator to record AEs, SAEs and pregnancies, as well as the time period for detecting and recording of the different events. Refer to Section [8.4](#) for guidelines and how to report SAE and pregnancy reports to GSK.
- The subjects will be instructed to contact the investigator immediately should they manifest any signs or symptoms they perceive as serious.
- At the vaccination visit (Visit 1), the first diary card will be provided to the subjects. The subject will be instructed to measure and record body temperature at home (using GSK supplied thermometers) and any solicited local/general AEs, as well as unsolicited AEs and concomitant medications/products/vaccinations as from the time of vaccination up to Day 7. The subject will be instructed to return the diary card to the investigator at the next study visit (Visit 2).
- A second diary card will be provided to the subject at Day 8 (Visit 2) to record any unsolicited AEs and concomitant medications/products/vaccinations from Day 8 until Day 30. The subject will be instructed to return the completed diary card to the investigators at the next study visit (Visit 3).
- The investigator will collect and verify completed diary cards during discussion with the subject and transcribe the information into the eCRF (in English) at Visit 2 and Visit 3.
- Any unreturned diary cards will be sought from the subject through telephone call(s) or any other convenient procedure.

5.6.18. Extension/Booster study

It is likely that the RSV antibodies elicited by the vaccine may wane during the period between pregnancies, therefore there may be a need to administer the vaccine during each pregnancy to achieve optimal anti-RSV antibody levels in the neonate. In order to assess whether a booster dose might induce a higher reactogenicity or immune-tolerance, subjects who participated in the study RSV MAT-001 study may be invited to participate in a booster study.

The investigator will ask each subject, at the time of informed consent, if she is interested in participating in a booster study and will document this in the source documents only. At study conclusion (Day 181 contact), the investigator will confirm subject's interest and report it in the eCRF.

If a subject is not interested in participating in the booster study, the reason for refusal will also be documented in the subject's eCRF. Refusal to participate in the extension study will not prevent subjects from enrolling in the RSV MAT-001 study.

5.6.19. Day 181 Contact

Contact should be preferably performed via telephone, or alternatively, if phone contact is not possible, through email/other means where the information can be fully collected. When the contact is not done by telephone, if questions remain, the study site may follow-up with the subject via telephone.

During this contact, the investigator (or delegate) will ask the subject if she has experienced any serious adverse events and/or any AEs leading to study withdrawal since Visit 5 and/ or whether she has become pregnant. The investigator (or delegate) will also ask the subject for concomitant vaccinations/products/medications that she has received since Visit 5.

Subject's interest in participating in a booster study will also be re-confirmed at Day 181 contact, and the corresponding information will be reported in the eCRF (refer to Section 5.6.18).

Please refer to the SPM for further guidance.

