While pregnancy itself is not considered an AE or SAE, any adverse pregnancy outcome or complication or elective termination of a pregnancy for medical reasons will be recorded and reported as an AE or a SAE.

Note: The pregnancy itself should always be recorded on an electronic pregnancy report.

The following should always be considered as SAE and will be reported as described in Sections 8.4.1 and 8.4.3:

- Spontaneous pregnancy loss, including:
 - spontaneous abortion, (spontaneous pregnancy loss before/at 22 weeks of gestation)
 - ectopic and molar pregnancy
 - stillbirth (intrauterine death of foetus after 22 weeks of gestation).
- Any early neonatal death (i.e. death of a live born infant occurring within the first 7 days of life).
- Any congenital anomaly or birth defect (as per [CDC MACDP] guidelines) identified in the offspring of a study subject (either during pregnancy, at birth or later) regardless of whether the foetus is delivered dead or alive. This includes anomalies identified by prenatal ultrasound, amniocentesis or examination of the products of conception after elective or spontaneous abortion.

Furthermore, any SAE occurring as a result of a post-study pregnancy AND considered by the investigator to be reasonably related to the investigational vaccines will be reported to GSK as described in Section 8.4.3. While the investigator is not obligated to actively seek this information from former study participants, he/she may learn of a pregnancy through spontaneous reporting.

8.3. Detecting and recording adverse events, serious adverse events and pregnancies**8.3.1. Time period for detecting and recording adverse events, serious adverse events and pregnancies**

All AEs starting within 30 days following administration of the study vaccine (Day 1 to Day 30) must be recorded into the appropriate section of the eCRF, irrespective of intensity or whether or not they are considered vaccination-related.

The time period for collecting and recording SAEs will begin at the receipt of the study vaccine and will end at the contact at Day 181. See Section [8.4](#) for instructions on reporting of SAEs.

All AEs/SAEs leading to withdrawal from the study will be collected and recorded from the time of the receipt of the study vaccine.

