9. SUBJECT COMPLETION AND WITHDRAWAL

9.1. Subject completion

A subject who is available for Contact 1 at Day 181 foreseen in the protocol is considered to have completed the study.

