10.2. Secondary endpoints

- Occurrence of SAEs from vaccination up to Day 91 and up to Day 181 for all subjects, in all groups.
- Humoral immune response to the investigational vaccine at Day 8, Day 31, Day 61 and Day 91 for all subjects in each investigational RSV vaccine group
 - RSV-A neutralising antibody (Nab) titres
 - RSVPreF3 IgG antibody concentrations

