10.6. Derived and transformed data

The study groups will be defined by treatment actually administered.

For a given subject and a given demographic variable, missing measurements will not be replaced.

Safety

- For a given subject and the analysis of solicited symptoms within 7 days post-vaccination, missing or non-evaluable measurements will not be replaced. Therefore the analysis of the solicited symptoms based on the ES will include only vaccinated subjects for doses with documented safety data (i.e., symptom screen completed).
- For analysis of unsolicited adverse events (including SAEs) categorized by primary Medical Dictionary for Regulatory Activities (MedDRA) term, all vaccinated subjects will be considered. Subjects who did not report the event will be considered as subjects without the event.
- For the analysis of concomitant medications, all vaccinated subjects will be considered and analysis will be performed on the ES. Subjects who did not report the concomitant medication will be considered as subjects without concomitant medication.

Immunogenicity

- For a given subject and given immunogenicity measurements, missing or non-evaluable measurements will not be replaced. Therefore, an analysis will exclude subjects with missing or non-evaluable measurements.
- A seronegative subject is a subject whose antibody titre/concentration is below the cut-off value of the assay. A seropositive subject is a subject whose antibody titre/concentration is greater than or equal to the cut-off value of the assay.
- The Geometric Mean Titres/Concentrations(GMT/GMCs) calculations are performed by taking the anti-log of the mean of the log titre transformations. Antibody titres below the cut-off of the assay will be given an arbitrary value of half the cut-off of the assay for the purpose of GMT/GMC calculation. The cut off values are defined by the laboratory before the analysis and will be described in the Statistical Analysis Plan (SAP).

- In order to compute fold increase of antibody titres/concentrations (ratio) between post-vaccination and pre-vaccination titres/concentrations, antibody titres/concentrations below the assay cut-off will be given an arbitrary value of half the cut-off.
- The handling of data below the assay cut offs for GMT/GMC calculations will be described in the SAP.

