11.2.4. Safety

- For a given subject and the analysis of solicited symptoms within 7 days post-vaccination, missing or non-evaluable measurements will not be replaced. Therefore, the analysis of the solicited symptoms based on the Exposed Set will include only vaccinated subjects with documented safety data (i.e., symptom screen completed). More specifically the following rules will be used:
 - Subjects who documented the absence of a solicited symptom after vaccination will be considered not having that symptom after vaccination.
 - When a specific symptom is marked as having occurred following a specific vaccination (i.e. SDTM CE.CEOCCUR=Y for the specified post-vaccination period for the symptom in question), any missing daily recordings will be given imputed values to allow them to contribute to the 'Any' rows but not to specific grade rows of the symptom summary tables.
 - Dose without symptom sheets documented will be excluded.
- For analysis of unsolicited adverse events, such as serious adverse events or adverse events by primary MedDRA term, and for the analysis of concomitant medications, all vaccinated subjects will be considered. Subjects who did not report the event or the concomitant medication will be considered as subjects without the event or the concomitant medication respectively.

Note that for all tables described in this section, the way the percentage of subjects will be derived will depend on the event analysed (see table below for details). As a result, the N value will differ from one table to another.

Event	N used for deriving % per subject for Vaccination phase
Concomitant vaccination	All subjects with study vaccine administered
Solicited general symptom	All subjects with at least one solicited general symptom documented as either present or absent (i.e., symptom screen completed)
Solicited local symptom	All subjects with at least one solicited local symptom documented as either present or absent (i.e., symptom screen completed)
Unsolicited symptom	All subjects with study vaccine administered
Concomitant medication	All subjects with study vaccine administered

11.2.5. Number of decimals displayed:

The following decimal description from the decision rules will be used for the demography, immunogenicity and safety/reactogenicity.

Display Table	Parameters	Number of decimal digits
Demographic characteristics	Mean, median age	1
Demographic characteristics	SD (age)	1
Immunogenicity	Ratio of GMT/C	2

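### The Day 181 contact looks back only to Visit 5, so for a woman who missed Visit 5 its questions on SAEs and concomitant products skip a nominal 30 or 60 days

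*Protocol*

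**What the plan says.** Protocol 5.6.19 sets the Contact 1 questions. The first is whether the woman "has experienced any serious adverse events and/or any AEs leading to study withdrawal since Visit 5". A separate clause deals with pregnancy ("and/ or whether she has become pregnant"). A further question covers "concomitant vaccinations/products/medications that she has received since Visit 5". The first and third items carry the Visit 5 limit; the pregnancy clause carries no limit of its own. The section prefers telephone but allows email or other means, with a follow-up call optional, and refers to the Study Procedures Manual (SPM) for further guidance.

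Protocol 8.3.1 sets a continuous collection period that closes with Contact 1: "The time period for collecting and recording SAEs will begin at the receipt of the study vaccine and will end at the contact at Day" (the sentence ends with the day number, 181).

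Protocol 9.1 defines completion by Contact 1 alone: "A subject who is available for Contact 1 at Day 181 foreseen in the protocol is considered to have completed the study". Attendance at Visits 4 and 5 plays no part.

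The endpoint is in Protocol 10.2: "Occurrence of SAEs from vaccination up to Day 91 and up to Day 181 for all subjects, in all groups". For its analysis, Protocol 10.6 keeps all vaccinated women in the denominator and states: "Subjects who did not report the event will be considered as subjects without the event". SAP 11.2.4 repeats the rule and extends it to medication: "Subjects who did not report the event or the concomitant medication will be considered as subjects without the event or the concomitant medication respectively".

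**The concern.** The look-back starts at a fixed visit, not at the last time the woman was actually asked. For a woman who attended Visit 5 the two coincide. For a woman who missed Visit 5 but is reached at Day 181, they do not: the specific instruction for that contact starts the clock at a visit she did not attend. Any SAE, AE leading to withdrawal or concomitant product between her last attended visit and Day 91 then falls outside the question as worded.

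Nothing in the data would flag this. She is a completer, and her silence about that interval is analysed as absence of an event. Diary cards end at Day 30 (Protocol 5.6.17), so from then on detection rests on questioning and self-report. This is a first-in-human study with about 125 women per group, SAEs are expected to be few, and the third planned iSRC review covers safety to at least Day 91 (Protocol 8.10.2). A single missed SAE would change a group's count.

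**Working it through.** **1. Which attendance patterns leave a gap.** Nominal visit days are 31, 61, 91 and 181 (Protocol Tables 4 and 5). The general AE question in Protocol 8.3.3.1 reaches back to vaccination or to the previous visit.

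| Visits missed | Covered by | Not covered by the Contact 1 wording |
|---|---|---|
| Visit 4 only | Visit 5, asking back to the previous visit | 0 days |
| Visit 5 only | Visit 4, then Contact 1 from Day 91 | 91 − 61 = 30 days |
| Visits 4 and 5 | Visit 3, then Contact 1 from Day 91 | 91 − 31 = 60 days |

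The gap therefore needs Visit 5 to be missed. For such a woman it is 30/180 = 16.7% or 60/180 = 33.3% of follow-up to Day 181. For the Day 91 SAE endpoint it is 30/90 = 33.3% or 60/90 = 66.7%.

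**2. Share of all follow-up.** The documents give no missed-visit rate. Assume that 2-10% of 500 women miss Visit 5, with or without Visit 4, and are reached at Contact 1.

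- Low end: 10 women × 30 days = 300 person-days.
- High end: 50 women × 60 days = 3,000 person-days.
- To Day 181: 500 × 180 = 90,000 person-days, so 0.3% to 3.3%.
- To Day 91: 500 × 90 = 45,000 person-days, so 0.7% to 6.7%.

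**3. Effect on detection.** Protocol 10.4 gives an 80% or 90% chance of at least one AE among 125 women at a true incidence of 1.3% or 1.8%. Reproducing it with 1 − (1 − p)^125 gives 80.5% at p = 0.013 and 89.7% at p = 0.018, in agreement with the plan.

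Now treat p as an SAE incidence to Day 181 with constant hazard, and suppose that nothing in the gap is ever captured by another route. Both are assumptions, and the second is pessimistic. With m the fraction missing Visit 5 and f the gap divided by 180, the observable incidence is p(1 − m·f).

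| m | f | Relative undercount m·f | Detection at 1.3% | Detection at 1.8% |
|---|---|---|---|---|
| 0 | – | 0 | 80.5% | 89.7% |
| 2% | 30/180 | 0.3% | 80.4% | 89.6% |
| 10% | 60/180 | 3.3% | 79.4% | 88.9% |
| 20% | 60/180 | 6.7% | 78.3% | 88.0% |

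The last row goes beyond the assumed range as a stress case.

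**4. Expected number missed.** At 1.3%, 500 × 0.013 = 6.5 women would have an SAE. Multiplying by the undercount gives 6.5 × 0.0033 = 0.02 to 6.5 × 0.0333 = 0.22 missed across the trial.

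**The case against.** The strongest reply is that Contact 1 is not the only route. Collection under 8.3.1 is continuous whatever 5.6.19 says. The general question in 8.3.3.1 is described as the consistent method and reaches back to the previous visit. Section 6.6 requires questioning about medications and vaccinations at each visit or contact, with no look-back limit. Section 9.2.1 requires at least three documented attempts to contact women who do not return for scheduled visits, and 5.6.17 tells women to call at once about anything they perceive as serious. Attendance by visit and group is tabulated (SAP Template 3), so missed visits are visible. The SPM may already deal with a missed Visit 5, and a sensible caller might ask about the whole interval anyway.

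Most of this stands, and it rules out saying that such a woman is never asked. It does not remove the inconsistency. The 8.3.3.1 question is offered as an example, whereas 5.6.19 is the specific instruction for this contact and is narrower. Section 9.2.1 requires attempts at contact, not SAE questioning once contact is made. Self-report depends on what the woman perceives as serious. If the contact is by email, a written question is likely to be answered as worded. The SPM is not among the documents; if it is better, the protocol should match it.

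Four stronger readings might be inferred, and the documents do not support them:

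- **Missing Visit 4 alone leaves a gap.** It does not when Visit 5 is attended.
- **Pregnancies in the gap are lost.** The pregnancy clause has no Visit 5 limit, and 8.3.1 collects pregnancies from vaccination to Day 181.
- **The per-protocol immunogenicity sets are compromised.** They are defined by time-point. A woman who missed Visit 5 has no Day 91 result and is already out of that set; if she attended Visit 4, products up to then were asked about there. At most the concomitant-medication summaries are touched.
- **Loss differs by group.** Nothing in the documents links tolerability of a single dose, with solicited reactions collected over Days 1-7, to skipping a visit about three months later.

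**Conclusion.** The point holds in a limited form. For a woman who missed Visit 5 but is reached at Day 181, the wording of 5.6.19 leaves a nominal 30 or 60 days outside the questions on SAEs, AEs leading to withdrawal and concomitant products. That conflicts with the continuous SAE collection in 8.3.1, and the analysis rule turns any resulting silence into no event.

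The expected effect is small: about 0.3-3.3% of person-days to Day 181, and well under one missed SAE across the trial at the illustrative 1.3% incidence. These figures rest on an assumed 2-10% of women missing Visit 5. The expected SAE count also assumes a constant hazard and no capture by any other route, so it is an upper figure for a given missed-visit rate. The reason to act is that the loss would be silent, would concern rare serious events in a first-in-human study, and is avoidable. Minor priority.

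**What to change.** In Protocol 5.6.19, replace the Visit 5 anchor in both places (the SAE and AE-leading-to-withdrawal question, and the concomitant products question) with *since the last visit or contact at which this information was collected*. This makes 5.6.19 agree with 8.3.1. Check that the SPM guidance for Contact 1 says the same.

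The cost is one phrase, used twice, plus the SPM check. There is no extra contact and no new data field. For women who attended Visit 5 and gave the information there, nothing changes.

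One limit remains. An SAE first learned of at Contact 1 will correct the final analysis, including its count to Day 91, but it may come too late for the Day 91 analysis and the third iSRC review if Contact 1 falls after that data cut.
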